9.5. Single reference safety document

A Single Reference Safety Document (SRSD) refers to a document that contains the information on the known safety profile. The package insert of this product will be the SRSD in this study. Pfizer Japan Inc. will evaluate the safety information reported by the investigator during the investigation period using the SRSD.

The investigator will also prescribe the drug and give the drug administration guidance based on the SRSD.

10. PLANS FOR DISSEMINATING AND COMMUNICATING STUDY RESULTS

The study results may be published during scientific meetings, in research paper, etc. for the purpose of providing proper use information, etc.

COMMUNICATION OF ISSUES

In the event of any prohibition or restriction imposed (e.g., clinical hold) by an applicable Competent Authority in any area of the world, or if the investigator is aware of any new information which might influence the evaluation of the benefits and risks of a Pfizer product, Pfizer should be informed immediately.

In addition, the investigator will inform Pfizer immediately of any urgent safety measures taken by the investigator to protect the study patients against any immediate hazard, and of any serious breaches of this NI study protocol that the investigator becomes aware of.

13. OTHER NECESSARY MATTERS

1) Amendment of the protocol

Based on the new knowledge to be obtained according to the progress of this study, the need for amendment of the protocol will be examined and the protocol will be amended if necessary. Also, the need for amendment of the protocol will be examined and the protocol will be amended as necessary even if the partial change in the dosage and administration or indication is approved during the reexamination period (except the case when the reexamination period is newly designated), etc.

2) Actions to be taken if any problem or question is observed

In the cases where the onset of any serious and unknown adverse reaction is suggested, a significant increase in the frequency of adverse reactions is observed, any problem is found in the effectiveness and safety of the drug compared to those prior to the approval, the onset of a different kind of adverse reaction is suggested, etc.,

[REDACTED]

implementation of a special drug use investigation or post-marketing clinical study should be considered to detect or confirm the cause and to verify the assumption, etc. derived from the deliberations.

16. LIST OF TABLES

- Page 8. Table 1. Variables/schedule of observation

17. LIST OF FIGURES

N/A

18. LIST OF STAND ALONE DOCUMENTS

N/A

19. ADDITIONAL INFORMATION

N/A

1. AMENDMENTS FROM THE PREVIOUS VERSION

Version	Date	Author(s)	Summary of Changes/Comments
1.0	22-OCT-2014	PPD [Redacted]	Initial version
2.0	04-OCT-2017	PPD [Redacted]	
Study status: Ongoing
 
5.1 Safety Analysis Set
 
 - Changes were made to coordinate with the revision of the “Guidance for Criteria for Inclusion in Analysis Sets and Handling of Data in Drug Use Investigations”. 
5.2.1. Cyst Analysis Set
 
 - Non-target disease of the study was added to the criteria for patients to be excluded. 
5.2.2. Clinical Response Analysis Set
 
 - Non-target disease of the study was added to the criteria for patients to be excluded. 
5.3. Subgroups
 
 - Categories that serve as a reference in comparisons between subgroups were underlined. - Items of subgroups were added. - A description on patients who may meet contraindications in the package insert of this drug was added. - The SMQs of the definitions of hepatic dysfunction and renal dysfunction were changed to the narrow scope only. 
6.1. Safety Endpoints
 
 - Based on the results of internal review, adverse drug reactions were changed to adverse events determined to be related to AMEPAROMO by the investigator. 
8.1.3. Analysis of Binary Data
 
 - Calculation of risk difference and 95% confidence interval were added to analyses between subgroups, and graphical presentation of risk ratio was deleted. 
8.2.2. Patient Background and Treatment History of AMEPAROMO
 
 - Other diagnostic names and the description of prior medications other than those for intestinal amebiasis were added to patient background. - The presence or absence of overdose and the definition of overdose were added to the status of treatment of AMEPAROMO. 
8.2.3. Safety Analysis
 
 - The definition of main analysis period for safety analysis was added.

090177e1918e8907\Approved\Approved On: 26-Jul-2019 07:07 (GMT)

Version	Date	Author(s)	Summary of Changes/Comments
			
8.2.3.1. Adverse Drug Reactions
 
 - A statement was added to note that the listing of contraindicated patients will be prepared and adverse drug reactions will be tabulated by SOC and PT by patients who do or do not meet contraindications, as necessary. - The status of development of adverse drug reactions by whether they developed within or outside of the observation period was added. 
8.2.3.4. Subgroup Analysis
 
 - Risk difference was added to analyses between subgroups. - The analysis of serious adverse drug reactions and the analysis of risk ratio and risk difference of serious adverse drug reactions were deleted. 
8.2.4.3. Subgroup Analysis
 
 - The description of subgroup analysis was clarified. 
9. LISTINGS
 
 - The listing of contraindicated patients was added. 
10. APPENDIX
 
 - Appendix 1 was deleted. 
Other description adjustments were made.

3.0	10-SEP-2018	PPD [REDACTED]	
Study status: Ongoing
 
2.1. Study Design
 
 - A description on design and registration system was modified in association with a protocol amendment. 
5.3. Subgroups
 
 - Clinical response evaluation to be performed when prior treatment for intestinal amebiasis is present was deleted from factors for subgroup analysis. - To examine the relationship between adverse drug reactions and concomitant medications, concomitant medications were added to subgroup analysis of safety as a factor. Concomitant medications here refer to drugs concomitantly used by the onset of the last adverse drug reaction observed during the observation period plus 28 days. 
6.1. Safety Endpoints
 
 - The definition of serious adverse events or adverse drug reactions was added as an endpoint. 
7. HANDLING OF MISSING DATA
 
 - A description on handling in the case the causal relationship of adverse events is missing was added. 
8.1.3. Analysis of Binary Data
 
 - A statement was added to note that risk ratio and risk

090177e1918e8907\Approved\Approved On: 26-Jul-2019 07:07 (GMT)

Version	Date	Author(s)	Summary of Changes/Comments
			
difference will not be calculated if the number of patients in subgroups compared is less than 10.
 
8.2.2. Patient Background and Treatment History of AMEPAROMO
 
 - The presence or absence of concomitant medication and prior treatment for intestinal amebiasis were added. - The definition of overdose was modified, and the definition was shown in a footnote. 
8.2.3. Safety Analysis
 
 - The tabulation and analysis period was changed from the observation period to the observation period plus follow-up period (28 days) as a result of review, and a description adjustment was made. - The status of development of adverse drug reactions by whether they developed within or outside the observation period was deleted because of the above change. 
8.2.3.4. Subgroup Analysis
 
 - A statement was added to note that the number and proportion of patients with adverse drug reactions will be tabulated by SOC and PT if the risk ratio is ≥ 2 or ≤ 0.5. - A statement was added to note that the number and proportion of patients with adverse events by age (elderly, non-elderly), presence or absence of hepatic dysfunction, presence or absence of renal dysfunction, and presence or absence of HIV infection will be tabulated by SOC and PT. 
8.2.3.5. Exploratory Analysis
 
 - An analysis was added to examine the relationship of concomitant medications with the development of adverse drug reactions. 
9. LISTINGS
 
 - The listing of concomitant medications by patient was added. - The listing of patients with overdose was added. - In accordance with PSEHB/PED Notification No. 1128-2 and PSEHB/PSD Notification No. 1128-4 “Partial Revision on Appendix Forms of Periodic Safety Update Reports and Their Entry Methods,” Appendix Form 2 to be prepared in periodic safety update reports was added, Appendix Form 2 was changed to Appendix Form 15, and Appendix Form 3 was changed to Appendix Form 16. 
Other description adjustments were made.

090177e1918e8907\Approved\Approved On: 26-Jul-2019 07:07 (GMT)

2. INTRODUCTION

This statistical analysis plan describes the statistical analysis plan for the drug use investigation of AMEPAROMO Capsules 250 mg (hereinafter referred to as AMEPAROMO). In this plan, sentences cited from the Protocol are shown in *Italics*.

2.1. Study Design

This investigation is a multicenter open study in patients who received AMEPAROMO for treatment of intestinal amebiasis. Patients who have never been treated with AMEPAROMO will be enrolled using a central registration system. The observation period shall start on the day the treatment with AMEPAROMO begins (Day 1) and end on Day 10. The main effectiveness analysis item will be the proportion of cyst negative based on the results of examination of cysts up to 3 months after the completion of observation period (or discontinuation of treatment), and clinical response assessed by the investigator will also be evaluated. A target sample size of 100 patients was selected. The rationale for the target sample size is shown below.

- *Rationale*

The number of patients who will receive AMEPAROMO may be extremely small, but 100 patients were chosen as a sample size that can be collected during a certain period of time from the viewpoint of the feasibility of the study.

2.2. Study Objectives

This study will be conducted to investigate the safety and effectiveness of AMEPAROMO in daily medical practice in terms of: 1) Adverse drug reactions unexpected from precautions (unknown adverse drug reactions); 2) Occurrence of adverse drug reactions under daily medical practice; and 3) Factors that may affect safety, effectiveness and other relevant matters.

3. INTERIM AND FINAL ANALYSIS

In this study, interim analyses for periodic safety update report will be performed periodically. At the time of interim analyses, only the analyses of items necessary for periodic safety update report among the statistical analyses specified in this plan will be performed. In addition, the final analysis for the application for reexamination will be performed. At the time of the final analysis, all analyses specified in this plan will be performed.

4. HYPOTHESES AND DECISION RULES

4.1. Statistical Hypotheses

Because this study is not a confirmatory investigation, the tests are considered as exploratory tests.

4.2. Statistical Decision Rules

Not applicable.

5. ANALYSIS SETS

5.1. Safety Analysis Set

The safety analysis set is the full analysis set that is as close as possible to all AMEPAROMO-treated patients. Specifically, the safety analysis set includes all registered or reported patients excluding any patients who meet any of the following criteria:

- a. The case report form (CRF) could not be collected at all (description in the report, “case report form not collected”)
- b. There was a violation or deficiency in the contract (description in the report, “contract violation/deficiency”)
- c. There was a violation of registration (description in the report, “registration violation”)
- d. Administration of the drug under investigation is not reported at all (description in the report, “no administration information”)
- e. Information on adverse events is not reported at all - no visits after the first prescription day (description in the report, “no adverse event information - no visits”)
- f. Information on adverse events is not reported at all - there is a visit after the first prescription day but no description of safety information (description in the report, “no adverse event information - no description”)

Details for each criterion should follow the “Guidance for Criteria for Inclusion in Analysis Sets and Handling of Data in Drug Use Investigations”.

5.2. Effectiveness Analysis Sets

There are two effectiveness analysis sets: the cyst analysis set, in which effectiveness will be determined based on the results of examination of cysts; and the clinical response analysis set.

5.2.1. Cyst Analysis Set

The cyst analysis set consists of the patients in the safety analysis set who have undergone the examination of cysts after AMEPAROMO treatment. Patients who meet any of the following criteria will be excluded:

- g. Examination of cysts has not been performed (description in the report, “no information on examination of cysts”)

- h. Non-target disease of the study (description in the report, “Non-target disease of the study”) [That is, “others” is checked with no other information in the CRF item that asks the disease (diagnosis) that required the use of AMEPAROMO.]

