5.2.2. Clinical Response Analysis Set

The clinical response analysis set consists of the patients in the safety analysis set in whom clinical response (assessed by the investigator) has been evaluated. Patients who meet any of the following criteria will be excluded:

- i. Information on clinical response assessment is not reported at all (description in the report, “no clinical response information”)
- j. Non-target disease of the study (description in the report, “Non-target disease of the study”) [That is, “others” is checked with no other information in the CRF item that asks the disease (diagnosis) that required the use of AMEPAROMO.]

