5.3. Subgroups

Subgroup analyses of safety will be performed for the following patient background factors. Underlined categories will be used as a reference in comparisons between subgroups.

- Sex [male, female]
- Children (<15 years), adults (≥15 to <65 years), elderly (≥65 years)
- Inpatient/outpatient status at the first prescription [inpatient, outpatient]
- Diagnostic name [intestinal amebiasis, others]
- Severity [mild, moderate, severe, unknown]
- Initial onset/recurrence [initial onset, recurrence]
- HIV infection [absent, present]
- Past medical history other than HIV infection [absent, present]
- Concurrent illness other than HIV infection [absent, present]
- Presence or absence of prior treatment for intestinal amebiasis [absent, present]
- Presence or absence of hepatic dysfunction [absent, present]
- Presence or absence of renal dysfunction [absent, present]
- Presence or absence of concomitant medication up to the development of adverse drug reactions^a [absent, present]

Subgroup analyses of safety will be performed for the other factors shown below.

- Pregnant and parturient women (pregnancy present)

^a: The presence or absence of concomitant medications will be determined by excluding concomitant medications started to be used after the day of onset of the last adverse drug reaction observed during the observation period plus 28 days.

- Overdose^b (overdose present)

Patients in whom AMEPAROMO might have been contraindicated per the package insert (hereinafter referred to as contraindicated patients) will be sampled from the registry according to separately-specified criteria and be analyzed for the safety of AMEPAROMO as a subgroup analysis.

Subgroup analyses of effectiveness will be performed for the following patient background factors. Underlined categories will be used as a reference in comparisons between subgroups.

- Sex [male, female]
- Presence or absence of hepatic dysfunction [absent, present]
- Presence or absence of renal dysfunction [absent, present]
- Children (<15 years), adults (≥15 to <65 years), elderly (≥65 years)
- Severity [mild, moderate, severe, unknown]
- Initial onset/recurrence [initial onset, recurrence]
- HIV infection [absent, present]
- Past medical history other than HIV infection [absent, present]
- Concurrent illness other than HIV infection [absent, present]
- Presence or absence of prior treatment for intestinal amebiasis [absent, present]

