8.2. Statistical Analysis

8.2.1. Overview of Patients

- **Number of sites by establisher and number of patients**

In CRF-collected patients, the number and proportion of sites by establisher shown below and the number and proportion of patients will be calculated.

- University hospitals
- National hospitals established by the Ministry of Health, Labour and Welfare
- Prefectural and municipal hospitals
- Public organizations
- Hospitals other than the above four established by corporations and individuals
- General practitioners/clinics

In addition, the mean, minimum, and maximum will be calculated for the number of patients per site.

- **Dispositions of patients**

In patients who registered to the study, the number of registered patients, the number of completed patients, the number of patients included in the analysis of safety, and the number of patients included in the analysis of effectiveness will be tabulated. In addition, the number of patients excluded from the analysis of safety and effectiveness and the number of patients by reason for exclusion will be tabulated.

- **Listing of discontinuations and dropouts**

In the safety and effectiveness analysis sets, the number and proportion of discontinued patients will be tabulated. In addition, the number and proportion of patients by reason for discontinuation will be tabulated.

- **Listing of excluded patients**

The listing of reasons for exclusion in patients excluded from the analysis of safety and effectiveness will be prepared.

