8.2.2. Patient Background and Treatment History of AMEPAROMO

- **Patient background**

In the safety and effectiveness analysis sets, the following patient background factors will be tabulated in accordance with Section 8.1.

- Sex [male, female]
- Age (continuous)
- Age group [<15 years, ≥15 to <65 years, ≥65 years]
- Inpatient/outpatient status at the first prescription [inpatient, outpatient]
- Body weight (continuous)
- Body Mass Index (continuous)
- Diagnostic name [intestinal amebiasis, others]
- Diagnostic name [details of others]
- Severity [mild, moderate, severe, unknown]
- Initial onset/recurrence [initial onset, recurrence]
- Hepatic dysfunction [absent, present]
- Renal dysfunction [absent, present]
- HIV infection [absent, present]
- Past medical history [absent, present]
- Concurrent illness [absent, present]
- Presence or absence of prior treatment for intestinal amebiasis [absent, present]
- Clinical response of prior treatment [effective, not effective, indeterminate]

In the safety analysis set, the number and proportion of the following patients will be tabulated by SOC and PT of MedDRA.

- Past medical history
- Concurrent illness

In the safety and effectiveness analysis sets, the number and proportion of the following patients will be tabulated.

- Presence or absence of concomitant medication [absent, present]
- Concomitant medication
- Concomitant non-drug therapy
- Prior medication for intestinal amebiasis
- Prior medication other than those for intestinal amebiasis

- **Status of treatment of AMEPAROMO**

In the safety analysis set, the following status of treatment of AMEPAROMO will be tabulated:

- Duration of treatment (continuous)
- Dose per single dose (continuous)
- Number of doses (continuous)
- Daily dose (continuous)
- Presence or absence of overdose^c [absent, present]

The duration of treatment is from the day of initial dose in the study to the last confirmed day of dosing including the treatment suspension period.

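### Read literally, SAP exclusion criteria h and j keep patients with a named disease other than intestinal amebiasis in both effectiveness sets, against the criteria's own heading

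*SAP*

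**What the plan says.** Protocol 7.7 leaves the definition of the effectiveness set to the SAP. The SAP builds two sets from the safety set: the cyst analysis set (5.2.1), which carries the main effectiveness item, and the clinical response analysis set (5.2.2). Criteria h and j, one in each section, have the same heading (non-target disease) and the same bracket. The bracket begins with *That is* and applies the exclusion where *others* "is checked with no other information in the CRF item that asks the disease (diagnosis) that required the use of AMEPAROMO".

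Other places that bear on the meaning:

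- SAP 1, entry for version 2.0, on both sets: "Non-target disease of the study was added to the criteria for patients to be excluded". It gives no further definition.
- SAP 2.1: "This investigation is a multicenter open study in patients who received AMEPAROMO for treatment of intestinal amebiasis".
- SAP 5.3: diagnostic name (intestinal amebiasis or others) is in the list of safety subgroup factors. It is not in the list introduced by "Subgroup analyses of effectiveness will be performed for the following patient background factors".
- SAP 8.2.2: the background tables for the safety and effectiveness sets include "Diagnostic name [details of others]".

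**The concern.** The heading and the bracket do not describe the same patients. On the literal wording, a patient known to have a different disease is kept, while a patient whose disease is unspecified is removed and reported as having a non-target disease. That reverses what the heading announces.

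At stake is the denominator of the main effectiveness item and of the clinical response rate. Under SAP 3, the final analysis supports the reexamination application. A programmer who follows the bracket and one who follows the heading could produce different sets under the same exclusion label. If the choice were made after the results were known, it could not be shown to be independent of them.

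**Working it through.** The plan gives no figure to reproduce. The sample size of 100 rests on feasibility alone (Protocol 7.5.2). The check is therefore textual, followed by an illustration of size.

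**Step 1. Entries in the diagnosis item under the two readings.** The literal reading takes the bracket to mean that nothing is written beyond the tick. The other reading takes it to mean that *others* is the only diagnosis indicated.

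| Entry | Literal reading | *Others* is the only entry |
|---|---|---|
| Intestinal amebiasis only | kept | kept |
| *Others*, nothing written | excluded | excluded |
| *Others*, another disease named | **kept** | **excluded** |
| *Others* plus intestinal amebiasis | kept | kept |

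The readings differ in the third row only.

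**Step 2. Which reading does the text support?**

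- For exclusion: the heading itself; the population in SAP 2.1; and the absence of diagnostic name from the effectiveness subgroups, although it is a safety subgroup factor.
- For the literal reading: the words of the bracket, and the tabulation of the details of *others* in the effectiveness sets (SAP 8.2.2). The second is weak evidence, because one shared list serves all the sets.
- No section states which reading applies.

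**Step 3. Can such patients reach the sets?** Yes. The only enrolment criterion is no previous AMEPAROMO (Protocol 7.2.1 and 7.6.2.1), and there are no exclusion criteria (Protocol 7.2.2). SAP 5.3 and 8.2.2 provide for *others* as a diagnosis category, so such patients were anticipated.

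**Step 4. Size.** Let p be the cyst-negative proportion in intestinal amebiasis, q the proportion in patients with another named disease, and f the share of such patients if they are kept. Then

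proportion if kept − proportion if excluded = [(1 − f)p + fq] − p = f(q − p).

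All inputs are assumed: 100 patients with a positive or negative result, p = 80%, q = 100%. Intervals are exact 95%, the method in SAP 8.1.3.

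- 5 such patients: f(q − p) = 0.05 × 0.20 = 1 point. Excluded: 76/95 = 80.0% (70.5 to 87.5). Kept: 81/100 = 81.0% (71.9 to 88.2).
- 10 such patients: 0.10 × 0.20 = 2 points. Excluded: 72/90 = 80.0% (70.2 to 87.7). Kept: 82/100 = 82.0% (73.1 to 89.0).
- None: f = 0, so the shift is 0.

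With fewer evaluable patients the same count is a larger share. For 10 in 80 the shift is 0.125 × 0.20 = 2.5 points: 56/70 = 80.0% (68.7 to 88.6) against 66/80 = 82.5% (72.4 to 90.1).

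**The case against.** The strongest reply is that the bracket explains its heading and should be read with it. On that view nobody would keep a patient with a known non-target disease under a rule headed non-target disease. The labels support this: criteria for absent data carry labels such as "no administration information" (d) and "no clinical response information" (i), whereas h and j carry a disease label. An analyst who holds the CRF, and can see whether several boxes may be ticked and whether *others* has a text field, may find nothing unclear. Off-indication use may also be rare, since Protocol 7.2.1 gives intestinal amebiasis as the only indication and Protocol 9.5 has investigators prescribe according to the package insert. The tests are exploratory and there are no decision rules (SAP 4.1 and 4.2). SAP 8.2.1 already plans counts and a listing of exclusions.

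Most of this stands. It makes exclusion the likelier intention and the effect probably small. It does not remove the defect: the operative words still keep these patients, and a set definition should not need an outside form to be applied. The planned exclusion tables would help to expose the effect of whichever rule was used, but they do not fix the rule in advance.

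Two stronger readings are tempting. A reader might infer that the sponsor means to count patients with other diseases in the main effectiveness result; the heading and SAP 2.1 point the other way. A reader might also set q = 0 in the formula and report a fall of 4 points (0.05 × 0.80) or 8 points (0.10 × 0.80). That needs every patient with another disease to be cyst positive after treatment, which nothing in the documents supports.

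**Conclusion.** The point holds as a defect of wording in the analysis-set rule, and it is minor. Applied as written, h and j keep patients with a named non-target disease in both effectiveness sets. The context suggests that they were meant to be excluded, but the SAP does not say so.

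The size cannot be determined, because the documents give neither the number of such patients nor their cyst results. The illustrated shifts of 1 to 2 points for 5 or 10 patients in 100 assume p = 80% and that all of these patients are cyst negative. They are small beside exact intervals about 16 to 17.5 points wide. The direction is also an assumption: the documents do not show a bias in either direction, and with no such patients the two readings give the same result. The remaining uncertainty is the CRF, which may show how the item is laid out.

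**What to change.** Reword h and j to exclude every patient whose recorded diagnosis is not intestinal amebiasis, and state each case:

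- *others* only, with a named disease: excluded, unless review finds that the text describes intestinal amebiasis;
- *others* only, with nothing written: excluded;
- *others* plus intestinal amebiasis: kept.

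State that any review of the *others* text is completed before database lock, by someone without knowledge of the cyst or clinical response results, so that membership cannot depend on outcome. Align the diagnostic-name rows for the effectiveness sets in SAP 8.2.2 with the rule.

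The cost is about a line of SAP text in each criterion, an edit to the table list and a short text review. The disease name is already recorded (Protocol 7.3.1). SAP 8.2.1 already provides that "the number of patients by reason for exclusion will be tabulated", so the number affected will be visible without a new table. The endpoint definitions and the safety set do not change, so the clause in Protocol 7.7 on major modifications should not be triggered.
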